5.1.2.8 End of Treatment Visit (30 days post last dose)

- ECOG
- Medical history
- Physical exam
- Vital Signs
- Weight
- CBC with differential
- CMP

- Research tubes (2 purple top tubes for banking)
- Return all study drug in subject possession.
- Adverse event assessment

[figure not shown]
5.2. Treatment Administration

All treatment will be administered on an outpatient basis. See section 5.2.1 and 5.2.2 for special precautions relevant for each specific study agent administration. All therapy will be administered in cycles with each cycle consisting of 28 days.

Enrolled subjects will initiate umbralisib monotherapy for a one cycle lead-in defined by Cycle -1. This cycle is designed to allow for correlative assay sample collection to assess early clonal shifts after umbralisib therapy. Without the lead-in these shifts may otherwise be masked by peripheral elimination of circulating tumor cells by anti-CD20 therapy. Subjects will be monitored closely upon initiation with a C-1D15 visit to assess tolerability of umbralisib monotherapy. Upon completion of Cycle -1 subjects will then continue on daily umbralisib and initiate combination therapy with ublituximab (U2). Ublituximab administration and induction/continuation is defined in Section 5.2.1. Ublituximab will only be administered through Cycle 6 (i.e no maintenance administration). Starting at C7D1 enrolled subjects will continue on umbralisib monotherapy. Umbralisib will be given on a continuous once daily basis starting at Cycle -1 for each 28 cycle until disease progression, discontinuation due to toxicity, subject death, subject withdrawal of consent, or investigator withdrawal. Administration schedule and timing of umbralisib administration in relation to ublituximab are further defined in Section 5.2.3. The overall treatment administration is depicted in the schema below Figure 1.

Subjects will be evaluated for objective response after completion of 6 cycles of combination therapy. Subjects with a response \geq PR will be allowed to continue on study (umbralisib monotherapy maintenance). A subject that does not meet objective response criteria by IwCLL 2018 guidelines outlined in Section 9.1 at C7D1 must be taken off study. See section 5.4.1 for further details in management of these subjects not meeting strict response criteria after completion of combination therapy.

Figure 1. Study Drug Administration Schema

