5.1 Schedule of Evaluations

Table 1. Schedule of trial events

Schedule of Assessments				Year 1										
Study Procedure	Screening	C-1	C-1	Cycle 1				C2 D1	C3 D1	C4 D1	C5 D1	C6 D1	C7 D1	C10 D1
		D1	D15	Day 1	Day 2	Day 8	Day 15							
Informed Consent	X													
Inclusion/Exclusion	X													
ECOG	X	X	X	X				X	X	X	X	X	X	X
Demographics	X													
Medical History	X	X	X	X	X	X	X	X	X	X	X	X	X	X
Physical Exam	X	X	X	X	X			X	X	X	X	X	X	X
Vital Signs	X	X	X	X	X	X	X	X	X	X	X	X	X	X
Height	X													
Weight	X	X	X	X				X	X	X	X	X	X	X
EKG	X													
Bone Marrow Biopsy	X													
Bone Marrow Aspirate	X													
CBC with diff	X	X	X	X	X	X	X	X	X	X	X	X	X	X
Serum Chemistry (CMP) ^a	X	X	X	X	X	X	X	X	X	X	X	X	X	X
HIV Rapid Screen	X													
Hepatitis Antibody Screen ^b	X													
Cytomegalovirus (CMV) PCR	X										X			X
B-HCG ^c (FCBP only)	X													
Circulating DNA (research)		X		X				X						X
Clonal Evolution Analysis (research)		X		X				X						X
Ublituximab Infusion			X	X	X	X	X	X	X	X	X	X	X	
Umbralisib Dispensation		X	X	X				X	X	X	X	X	X	X
Adverse Event Monitoring ^d	At each timepoint AEs will be collected													
Radiologic Evaluation ^e	X							X						X

Schedule of Assessments	Year 2				Year 3+	EOT	Follow-up*
Study Procedure	C13 D1	C16 D1	C19 D1	C22 D1	C25 D1 then Every 3 months	30 days post last dose	Every 3 months
Informed Consent							
Inclusion/Exclusion							
ECOG	X	X	X	X	X	X	X
Demographics							
Medical History	X	X	X	X	X	X	X
Physical Exam	X	X	X	X	X	X	X
Vital Signs	X	X	X	X	X	X	X
Height							
Weight	X	X	X	X	X	X	X
EKG							
Bone Marrow Biopsy							
Bone Marrow Aspirate							
CBC with diff	X	X	X	X	X	X	X
Serum Chemistry (CMP) ^a	X	X	X	X	X	X	X
HIV Rapid Screen							
Hepatitis Antibody Screen ^b							
Cytomegalovirus (CMV) PCR	X	X	X	X	X		
B-HCG ^c (FCBP only)							
Circulating DNA (research)	X		X		X	X	
Clonal Evolution Analysis (research)	X		X		X	X	
Ublituximab Infusion							
Umbralisib Dispensation	X	X	X	X	X		
Adverse Event Monitoring ^d	At each timepoint AEs will be collected						
Radiologic Evaluation ^e	X		X				X (q12mo)

Footnotes:

- * Subjects who discontinue treatment due to toxicity, but have not progressed will continue in study follow-up. Visits should occur q3months after EOT visit or until subsequent non-study drug administration. Patients who discontinue treatment due to progression of disease will enter survival follow-up. Survival follow-up will be documented by phone call every 6 months up to 5 years.

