5.2.1 Ublituximab

Ublituximab infusions will be administered as an outpatient and consistent with previous Phase II and Phase III dosing schemes. During Cycle 1, infusions will occur on Day 1, Day 2, Day 8, and Day 15. On days 1 and 2 the 900mg will be split, with each subject receiving 150mg on day 1 and the remaining 750mg on day 2. All subsequent infusions starting from Cycle 1 Day 8 will consist of a single 900mg infusion of ublituximab. After completion of Cycle 1, dosing of ublituximab will occur on a monthly basis (q28 days) on day 1 of Cycles 2-6 (+/- 3 days). Starting at Cycle 1 Day 1 through Cycle 6 Day 1 ublituximab infusions will be in combination with oral administration of umbralisib. After 6 cycles of combination treatment, ublituximab infusions will be stopped and subjects will continue on umbralisib monotherapy. Titration schedules should follow the schema depicted in the Table 2. Upon completing Cycle 6 ublituximab infusions will be completed and subjects will not receive maintenance ublituximab. Subjects will continue with umbralisib monotherapy as described in Section 5.2.3.

Subjects will be eligible to start a new cycle of combination therapy with ublituximab unless they are experiencing toxicity requiring treatment delay as outlined in Section 6.2 Table 4.

Ublituximab should not be administered as an IV push or bolus. All subjects must be premedicated before ublituximab infusion with an antihistamine (diphenhydramine 50mg or equivalent), and a corticosteroid (dexamethasone 20 mg or equivalent dose) as follows:

- If pre-medications are administered IV: start the ublituximab infusion 30 minutes after conclusion of the last pre-medication infusion. If IV premedications are given over longer than a 30 minute timeframe per institutional standards, begin ublituximab within 10 minutes of stop time of last pre-medication.
- If pre-medications are administered orally: start the ublituximab infusion 45-60 minutes after ingestion of the oral pre-medications
- Adjusting antihistamine and corticosteroid doses, adjusting the timing of administration and/or additional pre-medications may be used at investigator discretion for additional prophylaxis against infusion related reactions

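### Table 1 appears to mark 11 ublituximab infusion visits where the text gives nine; the row needs checking against the source table and reconciling with the text

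*Combined protocol and SAP*

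**What the plan says.** The narrative gives one schedule throughout.

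- Section 5.2.1, Cycle 1: "During Cycle 1, infusions will occur on Day 1, Day 2, Day 8, and Day 15".
- Section 5.2.1, later cycles: "dosing of ublituximab will occur on a monthly basis (q28 days) on day 1 of Cycles 2-6 (+/- 3 days". The same section bounds the combination period: "Starting at Cycle 1 Day 1 through Cycle 6 Day 1 ublituximab infusions will be in combination with oral administration of umbralisib".
- Section 5.2: "Ublituximab will only be administered through Cycle 6 (i.e no maintenance administration". It makes Cycle -1 an umbralisib-only lead-in and returns subjects to umbralisib alone from C7D1. It refers the reader to Section 5.2.1 for how ublituximab is given.
- The synopsis (Drug Administration and Study Schedule) lists the same infusion days.
- The visit lists for Cycle -1 Day 15 (5.1.2.2) and for Cycle 7 onward (5.1.2.7) include umbralisib dispensing and no infusion.

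Section 5.2 also explains why the lead-in is kept free of antibody: "Without the lead-in these shifts may otherwise be masked by peripheral elimination of circulating tumor cells by anti-CD20 therapy".

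Table 1 (Section 5.1) reads differently. Its Year 1 row is "Ublituximab Infusion X X X X X X X X X X X", under visit columns whose right-hand part is "C2 D1 C3 D1 C4 D1 C5 D1 C6 D1 C7 D1 C10 D1". The row has no marks from Year 2 onward.

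**The concern.** A schedule of events is a natural place to look up what happens at a visit, and here it seems to disagree with the text on when an intravenous investigational antibody is given. Two visits are at issue.

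**Cycle -1 Day 15.** An infusion here would fall inside the lead-in, at a visit that Section 5.2 uses to judge tolerability of umbralisib alone, and before the C1D1 research sample. It would also come before the split first dose on C1D1 and C1D2. Neither Section 5.2.1 nor Table 2 gives a dose or rate for a Cycle -1 infusion. Which visit carries the first infusion bears on safety: in the first-in-human study summarised in Section 2.4.5, 16 of 23 infusion reactions followed the first infusion.

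**Cycle 7 Day 1.** An infusion here would come after the combination phase that the text ends at Cycle 6, at the visit where Section 5.4.1 assesses response to completed combination therapy. Table 2 would not expose the conflict, because its last block covers Cycle 2 and all remaining infusions without naming a final cycle.

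**Working it through.** This is a count. No sample-size or power formula is involved.

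**Step 1: visits in the text.** The text prints no total, but it lists the days. Cycle 1 has Days 1, 2, 8 and 15, which is 4 visits. Cycles 2 to 6 have Day 1 only, which is 5 visits. Total: 4 + 5 = 9.

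**Step 2: marks in Table 1.** Year 1 has 14 visit columns: Screening, C-1D1, C-1D15, C1D1, C1D2, C1D8, C1D15, C2D1, C3D1, C4D1, C5D1, C6D1, C7D1, C10D1. The ublituximab row has 14 cells: 2 blank, 11 marked, 1 blank. Matched cell to column, the marks run from C-1D15 to C7D1.

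**Step 3: comparison.** Marked in the table but not in the text: C-1D15 and C7D1. In the text but not marked: none. 11 − 9 = 2, and 2/9 = 22%.

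**Step 4: could the row simply have shifted?** An unbroken run of 11 marks fits 14 columns in four ways:

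| Run starts at | Run ends at | Marks outside the text's nine visits |
|---|---|---|
| Screening | C5D1 | 3 (Screening, C-1D1, C-1D15), and C6D1 is missed |
| C-1D1 | C6D1 | 2 (C-1D1, C-1D15) |
| C-1D15 (as read) | C7D1 | 2 (C-1D15, C7D1) |
| C1D1 | C10D1 | 2 (C7D1, C10D1) |

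At least two marks fall outside the text's schedule in every case. A shift changes which visits are surplus but not that there is a surplus.

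**Step 5: how reliable are the column positions?** Other rows of the same table, compared with the visit lists:

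- Umbralisib dispensing and physical exam match the visit lists at every Year 1 visit.
- CBC is marked in all 14 columns, so it says nothing about alignment.
- ECOG is blank at C1D8 and C1D15, but Section 5.1.2.5 lists it on both days.
- The radiology row and the two research-sample rows have their last Year 1 mark at C10D1. Section 5.1.2.7 puts the scan and the tubes at Cycle 7.
- CMV PCR is marked at Screening, C5D1 and C10D1 only. Sections 5.1.2.6 and 5.1.2.7 list it for Cycles 2 to 6 and from Cycle 7 on.

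The count of 11 is therefore firmer than the placement at C-1D15 and C7D1. The placement is the natural reading of a row whose cell count equals that of the header, but it needs checking against the source table.

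**The case against.** The strongest reply is that this is one row of a table that already disagrees with the text elsewhere, set against a narrative that speaks with one voice and refers to Section 5.2.1 for administration. Table 2 starts at Cycle 1 Day 1, so a reader trying to prepare a Cycle -1 infusion would find no instructions. The row may also have been damaged in reading the PDF. Step 4 rules out a shift, but it cannot rule out a mark that was added or repeated.

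Much of this stands. The text is consistent, which lowers the chance of a dosing error, and the source table must be looked at first. The reply does not dispose of the point, because no rule in the protocol says that the text prevails over Table 1.

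A reader might infer more than the documents support:

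- *That sites are working to contradictory schedules, or that all 24 subjects face an extra infusion.* The cover page names one participating site, and the synopsis and Section 11.1 call the study single center (Section 2.2 says multi-center). Passing through a visit column is not the same as being dosed. The documents do not say that orders are built from Table 1, and they do not show that any extra dose was given.
- *That a study endpoint is compromised.* The masking argument concerns banked samples. Section 8 says that no specific correlative studies are planned, and no primary or secondary endpoint rests on those samples.

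**Conclusion.** The inconsistency holds as a conflict between a table and the text: 11 marked infusion visits in Table 1 as read, against nine in the synopsis, the visit lists and Sections 5.2 and 5.2.1. The difference is two visits, or 22% of the text's number. On the natural reading these are C-1D15, in the antibody-free lead-in, and C7D1, where monotherapy is said to begin.

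The count assumes that reading the PDF neither added nor repeated a mark. The two named visits also assume that the row is correctly aligned, and the mismatches in other rows make that less than certain. The point matters because it concerns when an intravenous antibody is given. It is not evidence of misdosing or of harm to the response analysis. Which schedule is clinically right is for the sponsor to state.

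**What to change.** 1. Check the ublituximab row against the source Table 1. If the printed table shows the text's nine visits, the point falls away.
2. If it does not, reconcile the row with Sections 5.1.2.2, 5.1.2.7, 5.2 and 5.2.1, so that table and text show the same infusion visits. The sponsor should confirm the list.
3. Have the study site check that any orders built from the table match the confirmed list.
4. While the table is open, compare the radiology, research-sample, CMV and ECOG rows with the visit lists.

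For ublituximab the cost is a correction to one table row, sent with the next amendment. It adds no procedures and does not change the analysis plan.

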5.2.1 Ublituximab

Ublituximab infusions will be administered as an outpatient and consistent with previous Phase II and Phase III dosing schemes. During Cycle 1, infusions will occur on Day 1, Day 2, Day 8, and Day 15. On days 1 and 2 the 900mg will be split, with each subject receiving 150mg on day 1 and the remaining 750mg on day 2. All subsequent infusions starting from Cycle 1 Day 8 will consist of a single 900mg infusion of ublituximab. After completion of Cycle 1, dosing of ublituximab will occur on a monthly basis (q28 days) on day 1 of Cycles 2-6 (+/- 3 days). Starting at Cycle 1 Day 1 through Cycle 6 Day 1 ublituximab infusions will be in combination with oral administration of umbralisib. After 6 cycles of combination treatment, ublituximab infusions will be stopped and subjects will continue on umbralisib monotherapy. Titration schedules should follow the schema depicted in the Table 2. Upon completing Cycle 6 ublituximab infusions will be completed and subjects will not receive maintenance ublituximab. Subjects will continue with umbralisib monotherapy as described in Section 5.2.3.

Subjects will be eligible to start a new cycle of combination therapy with ublituximab unless they are experiencing toxicity requiring treatment delay as outlined in Section 6.2 Table 4.

Ublituximab should not be administered as an IV push or bolus. All subjects must be premedicated before ublituximab infusion with an antihistamine (diphenhydramine 50mg or equivalent), and a corticosteroid (dexamethasone 20 mg or equivalent dose) as follows:

- If pre-medications are administered IV: start the ublituximab infusion 30 minutes after conclusion of the last pre-medication infusion. If IV premedications are given over longer than a 30 minute timeframe per institutional standards, begin ublituximab within 10 minutes of stop time of last pre-medication.
- If pre-medications are administered orally: start the ublituximab infusion 45-60 minutes after ingestion of the oral pre-medications
- Adjusting antihistamine and corticosteroid doses, adjusting the timing of administration and/or additional pre-medications may be used at investigator discretion for additional prophylaxis against infusion related reactions

Corticosteroid premedication should be given on day 1, 8 and 15 of cycle 1. Subsequent use of steroid premedication starting with cycle 2, will be left to investigator discretion and is not mandatory with these subsequent infusions in the absence of infusion related reactions with previous doses. Use of oral acetaminophen 650 mg (or equivalent) should be restricted to patients who experience fever or pyrexia after week 1 dose, or as clinically warranted. During infusion the following monitoring schema should be followed by nursing:

- a) Nurse should remain with the patient during the first 15 minutes of the infusion
- b) Nurses should monitor vital signs (temperature, BP, and HR) and assess for signs of infusion reaction every 15 minutes for the first hour, then every 30 minutes for the remainder of the infusion, and upon infusion completion

Table 2. Ublituximab Titration Schedules**Cycle 1 Day 1 & 2 infusion of 4 hours**

Cycle 1	Ublituximab Dose	Total volume to be infused	Infusion rate			
			T0 to T30min	T30min to T1H	T1H to T2H	T2H to T4H
Day 1	150 mg	250 mL	10 mL/H	20 mL/H	35 mL/H	100 mL/H
Day 2	750 mg	500 mL	10 mL/H	20 mL/H	85 mL/H	200 mL/H

Cycle 1 Day 8 & 15 infusion of 3 hours

Ublituximab Dose	Total volume to be infused	Infusion rate		
		T0 to T1H	T1H to T2H	T2H to T3H
900 mg	500 mL	50 mL/H	150 mL/H	300 mL/H

Cycle 2 and remaining infusions over 90 minutes

Ublituximab Dose	Total volume to be infused	Infusion rate	
		T0 to T30min	T30min to T90min
900 mg	500 mL	200 mL/H	400 mL/H

5.2.2 Management of Infusion Related Reactions

Since infusion-related hypotension may occur, antihypertensive medications should be held 12-24 hours prior to and throughout ublituximab infusion. Infusion related reactions including severe reactions have been reported with ublituximab administration in patients with CLL. Guidelines are provided below for patients who experience such reactions. Symptomatic infusion reactions, despite premedication, may be treated at the discretion of the treating physician, including but not limited to: oral acetaminophen 650 mg (or equivalent), corticosteroids, antihistamines, oxygen, and bronchodilators.

If an infusion related reaction is observed at any time during the ublituximab treatment, the treating investigator may reduce the infusion flow rate at their discretion.

The following are recommended infusion rate reduction/delay guidelines for patients who experience severe Infusion Related Reactions (IRR's) in which treatment should be interrupted. Final decision for infusion rate reduction/delay or discontinuation resides with the treating investigator.

1st or 2nd Infusion Interruption:

- Hold infusion and closely monitor patient, institute symptomatic medical management until resolution of IRR symptoms. Treating investigator must be notified by research team and documentation should occur in the patient chart.
 - Symptomatic medical management should include administration of acetaminophen, antihistamines, and/or corticosteroids for fever (temperature $>38^{\circ}\text{C}$) and/or chills
 - Physician may order meperidine for persistent rigors, caution to be exercised if

- patient is hypotensive and meperidine may contribute to ongoing hypotension.
- Administer antihistamines and/or corticosteroids for flushing, urticarial, pruritus, or angioedema
- Administer IV fluid boluses for hypotension
- Administer epinephrine, corticosteroids and antihistamines in the event of an anaphylactic reaction
- Following the judgment of the Investigator, and provided the patient is stable, the infusion may be resumed at half the previous rate.
- If the patient does not experience any further IRR symptoms, infusion rate escalation may resume at the increments and intervals as appropriate at the treatment cycle dose (see Section 5.2.1)
- For any Grade 4 infusion related reaction, ublituximab should be stopped indefinitely. Subjects that experience a Grade 4 infusion reaction will not be allowed to be rechallenged.

3rd Infusion Interruption (same day):

- Discontinue infusion for that day – monitor patient for resolution of all symptoms. Patient should have all vital signs completed as well as any other standard of care procedures completed as warranted by the Investigator prior to release of patient from study site.
- Administer symptomatic medical management as above.
- Any remaining diluted investigational product should be discarded.
- If the infusion discontinued is the Cycle 1 Day 1 infusion, administer the scheduled Cycle 1 Day 2 dose according to the protocol dosing schedule.
- For any Grade 4 infusion related reaction ublituximab should be stopped indefinitely. Subjects that experience a Grade 4 infusion reaction will not be allowed to be rechallenged.

5.2.3 Umbralisib

Umbralisib will be administered orally as four 200mg capsules taken once daily for a total daily dose of 800mg. Umbralisib should be taken within 30 minutes of starting a meal. All subjects will initiate a one cycle lead in prior to starting combination therapy with ublituximab, subjects will initiate taking umbralisib on Cycle -1 day 1 through Cycle -1 day 28. Starting on Cycle 1 day 1, subjects may take the dose of umbralisib before or after infusion with ublituximab but umbralisib must be taken within 30 minutes of starting a meal. Subjects will continue daily oral dosing of 800mg umbralisib for 28 days which will constitute a cycle. Subjects should try to take the drug at the same time each day throughout the trial. Subjects should be instructed to swallow the tablets whole and should not chew or crush them. If a dose of umbralisib is missed, it should be taken as soon as possible on the same day. If it is missed for a period of greater than 12 hours, it should be skipped for that day. If vomiting occurs, no attempt should be made to replace the vomited dose. Subjects will continue daily dosing of umbralisib until disease progression, toxicities, or study completion whichever comes first.

Subjects will be eligible to start a new cycle of either combination or monotherapy of umbralisib unless they are experiencing toxicity requiring treatment delay as outlined in Section 6.2 Table 4.

Umbralisib will be dispensed at the sites by the research coordinator or designee under the direction of the PI or by a pharmacist at the site. Before dispensing, the site pharmacist or authorized designee must check that the umbralisib is in accordance with the product specifications and the validity is within the re-test date. Immediately inform TG Therapeutics, Inc. at [contact] with any product quality concerns or questions.

Subjects must be provided drug in its original container. Subjects will be dispensed sufficient umbralisib for roughly 1 cycle of treatment. If the interval between visits is greater than 1 cycle, subjects may be given more than 1 cycle of umbralisib so that they do not have to return between scheduled visits. Subjects should be instructed to return all empty and partially filled bottles including any unused tablets when they return to the site. Study drug compliance should be reviewed with the subject at the beginning of each new treatment cycle and as needed.

